5.4 PRESENTATION OF RESULTS

5.4.1 *Calculation of descriptive statistics and percentages*

For continuous parameters, full descriptive statistics will only be presented if there are at least 2 non-missing observations. Alternatively, only the number of non-missing data points and mean are shown.

Descriptive statistics will include the number of non-missing data points, the arithmetic mean, the standard deviation (SD), the median, minimum and maximum.

Descriptive statistics of efficacy parameters will additionally include standard error (SE) and 95% confidence interval (CI) on the mean (based on t-distribution, without continuity correction). Descriptive statistics of antibody response will show geometric mean and corresponding 95% confidence interval (CI) rather than arithmetic mean. Geometric mean and CI are calculated as the exponentials of the arithmetic mean and corresponding CI (based on t-distribution, without continuity correction) of the log-transformed data. Descriptive statistics of T cell response will show 95% CI on the median (based on ranks) and not on the mean.

Survival estimates will include the arithmetic mean with its SE, the median, first and third quartiles with their 95% CI, and the number of subjects who are assessed, censored and who have an event.

Mean, median, SE, SD and CI will be presented with one more decimal place than the individual values, with a maximum of 5 decimal places. Minimum and maximum will be presented with the same number of decimal places than the individual values, with a maximum of 4 decimal places.

P-values will be presented with four decimal places, ratios with three decimal places and test statistics with two decimal places.

For event-type data, the denominator will be all subjects in the analysis set and phase, unless specified otherwise, in which cases a footnote to the table will specify the denominator. All treatments will be shown, even if no events are present.

For frequency tabulations and cross-tabulations, missing values will not be included in the denominator count when computing percentages. For cross-tabulations of post-baseline results versus baseline results, a 'missing' category will be shown for baseline results if applicable.

Percentages will be shown with one decimal place.

5.4.2 *Presentation of treatments*

The following treatment labels will be used in the tables, listings and figures:

- PLACEBO
- MVA-NP+M1
- OVERALL

	Statistical Analysis Plan	
FLU010	Final analysis	Final 3.0 of 15JUN2020

Overall is a grand total summarising all subjects over treatments, only shown for the general characteristics and adverse events analysis.

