2.2.4 Presentation of results

To assess the impact of missing DMSO replicates, all tables and figures on T-cell response will be prepared on two subsets of data (evaluated separately for NP and M1):

- Samples with at least 1 result
- Subset above, excluding samples with only 1 DMSO replicate result

Background subtracted and negative control T cell response results (IFN-gamma and granzyme B results; separately for NP, M1, NP+M1) will be summarised by means of descriptive statistics at each analysis visit. This will be done separately for the vaccination and challenge period. Actual values and changes from baseline will be tabulated separately.

T cell responder status will be presented in a frequency table at each analysis visit, separately for vaccination and challenge period.

Antibody response results will be summarised by means of descriptive statistics at each analysis visit. Actual values and changes from baseline will be tabulated separately. The ratio (MVA-NP+M1 / placebo) of the geometric means will also be shown with corresponding 95% CI.

Correlation of T cell responses, as assessed by the mean increase from baseline to post vaccination at day 8 and day 28 (for IFN-gamma and granzyme B results; separately for NP, M1, NP+M1), to the primary endpoint, symptom scores, and influenza incidence will be explored graphically, including Spearman correlation coefficients.

Graphs of the median actual values over time will be prepared for background subtracted and negative control IFN-gamma and granzyme B results (separately for NP, M1, NP+M1).

	Statistical Analysis Plan	
FLU010	Final analysis	Final 3.0 of 15JUN2020

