5.2 PHASES AND TIME POINTS

5.2.1 *Phases*

All events and assessments will be allocated to phases.

Phase	Start	End
Screening	Date of signing the ICF, with 00:00 added as time part	Vaccination date(time) – 1 minute
Vaccination	Vaccination date(time)	Challenge date(time) – 1 minute
Challenge	Challenge date(time)	End date of Day 28 post-challenge visit, with 23:59 added as time part
Follow-up	End of challenge phase + 1 minute	Date of last contact, with 23:59 added as time part

Per definition, and for each subject, the last available phase ends on the date of last contact (or the cut-off date for the topline analysis), with 23:59 added as time part.

AEs will be allocated to phases as described in section 3.1.2. All other assessments will be allocated to phases based on the assessment date(time).

In case of (partially) missing date(time) fields which cannot be allocated to a phase based on the available date(time) information, the visit label will be used to allocate to the correct phase. If this is not possible (unscheduled visits or visits on a turning point between phases), assessments will be allocated to the vaccination phase unless the available parts of the assessments start or stop date(time) provide evidence for allocating to the challenge/screening/follow-up phase.

5.2.2 *Baseline and change from baseline*

Baseline will be defined by phase.

The vaccination baseline value is the last available and non-missing value before the first administration of any study drug and will be used for data collected during the vaccination period.

The challenge baseline value is the last available and non-missing value before the administration of challenge inoculation and will be used for data collected during the challenge period.

Change from baseline is defined as follows:

Change from baseline at time point t = value at time point t – baseline value.

	Statistical Analysis Plan	
FLU010	Final analysis	Final 3.0 of 15JUN2020

5.2.3 *Relative day*

Relative days (DY) will be calculated both with respect to the vaccination and to the challenge, according to the following rule:

- Concerned date < reference date: DY = concerned date – reference date
- Concerned date \geq reference date: DY = concerned date – reference date + 1

The reference dates are the vaccination date and the date of challenge.

5.2.4 *Analysis visits*

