- Missing time will be imputed with challenge time - 5 min for morning samples and challenge time + 12 h for evening samples.
- Missing date will be imputed based on the scheduled timepoint: missing date on Day 3 = challenge date + 2 days

Partially missing date of event will be imputed as follows for the calculation of time to start and time to peak of viral shedding:

- Missing time will be imputed with challenge time - 5 min for morning samples and challenge time + 12 h for evening samples.
- Missing day will be imputed with 1
- Missing day and month will be imputed with 01JAN

	Statistical Analysis Plan	
FLU010	Final analysis	Final 3.0 of 15JUN2020

Partially missing date of event will be imputed as follows for the calculation of time to cessation of viral shedding:

- Missing time will be imputed with challenge time - 5 min for morning samples and challenge time + 12 h for evening samples.
- Missing day will be imputed with last day of the month
- Missing day and month will be imputed with 31DEC

Partially missing start and stop dates of events will be imputed as follows for the calculation of duration of viral shedding:

- Missing time will be imputed with challenge time - 5 min for morning samples and challenge time + 12 h for evening samples.
- Missing start day will be imputed with 1
- Missing start day and month will be imputed with 01JAN
- Missing stop day will be imputed with last day of the month
- Missing stop day and month will be imputed with 31DEC

Note: If imputation of the start date results in a start date posterior to the stop date / anterior to challenge, the start date will be imputed with the stop date / challenge date respectively. If imputation of the stop date results in a stop date anterior to the start date / posterior to date of last contact, the stop date will be imputed with the start date / date of last contact respectively.

5.3.3 *Values below or above a threshold*

Safety values expressed as below (or above) the detection limit will be imputed by the value of the detection limit itself. Listings will always show the non-imputed values.

Viral load values reported as $> XX$ will be imputed with XX . Viral load values reported as $< XX$ will be imputed with $XX/\sqrt{2}$. For values reported as 'not detected', the \log_{10} viral load will be imputed with 0.

Immunogenicity values reported as $> XX$ will be imputed with XX . Immunogenicity values reported as $< XX$ will be imputed with $XX/2$.

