14.2.4.3 T Cell Response Status (ELISpot Results) ITT
14.2.4.4 Antibody Response Actual Values Over Time ITT
14.2.4.5 Antibody Response Changes Over Time ITT

SAFETY

ADVERSE EVENTS

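### The geometric mean planned for antibody change from baseline is undefined for any participant whose titre does not rise, and the SAP has no rule for such values

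*SAP*

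**What the plan says.** Three current SAP rules meet in one table.

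- SAP 5.2.2 gives a single definition for all data: "Change from baseline at time point t = value at time point t – baseline value". For the challenge period, "The challenge baseline value is the last available and non-missing value before the administration of challenge inoculation". Titres are not treated separately.
- SAP 2.2.4 says of antibody results: "Actual values and changes from baseline will be tabulated separately. The ratio (MVA-NP+M1 / placebo) of the geometric means will also be shown". SAP 8.1 lists the resulting table, 14.2.4.5, as "Antibody Response Changes Over Time", on the ITT set.
- SAP 5.4.1 says: "Descriptive statistics of antibody response will show geometric mean and corresponding 95% confidence interval (CI) rather than arithmetic mean". It adds: "Geometric mean and CI are calculated as the exponentials of the arithmetic mean and corresponding CI" of the logged data. The change table is not exempted.

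Two further rules bear on how often the problem arises. SAP 5.3.3 replaces an immunogenicity value below the limit by half that limit. Protocol 4.1 admits only participants with an MNT below 20 against the challenge strain.

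The effect of vaccination on the antibody response after challenge is an exploratory objective (Protocol 2.3). Protocol 9.1.2.3 plans a descriptive ratio of MNT and HI GMTs between arms, based on the log10 difference. SAP 2.2.3 plans an ANCOVA on log Day 28 titres, back-transformed to a geometric mean ratio.

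**The concern.** A geometric mean needs strictly positive values. A raw difference in titre is zero when the titre does not move and negative when it falls. Read together, the rules ask for a statistic that cannot be computed for a group certain to exist in a challenge trial: those who are not infected or do not seroconvert.

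Since the SAP does not say what to do, the programmer must choose. Letting the software set the log to missing, adding a constant, or switching to log differences would give different answers. Under the first option, the geometric mean describes only those who rose. If the vaccine lowers the infection rate, the participants lost are those who carry the effect, and the change table could look similar in both arms while the log-titre ANCOVA shows a difference.

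Even among those who rise, a raw difference is a poor scale for titres: 5 to 40 and 10 to 80 are both 8-fold rises, but the changes are 35 and 70.

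**Working it through.** **1. Where the statistic fails.** The geometric mean is exp[(1/n) Σ log xᵢ], with xᵢ = Day 28 titre − challenge baseline titre. For 5 → 5, log(0) = −∞. For 10 → 5, log(−5) is undefined. One such participant is enough.

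**2. Why zeros will occur.** With half-limit imputation, a participant below the limit at both visits has a change of XX/2 − XX/2 = 0. The entry limit keeps MNT baselines low (it does not constrain HI). The protocol's reason for amending to version 5.0 notes that a twofold difference is within assay variability, so falls will occur too.

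**3. The plan's own figure.** The protocol synopsis and 9.1.2.3 expect about 20 of 80 vaccinees with a zero vAUC at 83% attack rate and 30% efficacy. 80 × 0.83 × 0.30 = 19.9 reproduces this, but it counts infections averted. All uninfected are n × [1 − 0.83 × (1 − E)], where E is efficacy against infection:

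| E | Vaccine (n=80) | Placebo (n=54) |
|---|---|---|
| 0% | 13.6 (17.0%) | 9.2 (17.0%) |
| 10% | 20.2 (25.3%) | 9.2 (17.0%) |
| 20% | 26.9 (33.6%) | 9.2 (17.0%) |
| 30% | 33.5 (41.9%) | 9.2 (17.0%) |

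For example, 80 × (1 − 0.83 × 0.70) = 33.5 and 54 × 0.17 = 9.2. At 0% efficacy the shares are equal; only the counts differ, because of the 3:2 allocation.

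**4. What loss of non-positive changes would do.** Simulation with 3,000 trials per setting. The following assumptions are not in the documents: assay limit 10; baseline 5 in 70% and 10 in 30%; rise in the infected centred on 4-, 8- or 16-fold with SD 1.2 log2 steps; in the uninfected either no movement, or 30% shifting one dilution (half up, half down). Titres cannot fall below 5. At 83% attack rate and 30% efficacy:

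| Rise if infected | Uninfected shifting | No positive change, vaccine / placebo | Ratio of geometric mean changes, positive changes only | Ratio of geometric mean fold-rises, everyone |
|---|---|---|---|---|
| 4-fold | 0% | 48.0% / 25.7% | 1.00 | 0.71 |
| 4-fold | 30% | 41.8% / 23.2% | 0.91 | 0.72 |
| 8-fold | 0% | 43.0% / 18.6% | 1.00 | 0.60 |
| 8-fold | 30% | 36.6% / 16.0% | 0.88 | 0.61 |
| 16-fold | 0% | 42.0% / 17.2% | 1.00 | 0.50 |
| 16-fold | 30% | 35.8% / 14.6% | 0.83 | 0.51 |

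Ratios are vaccine/placebo. At 0% efficacy about 15% to 26% have no positive change in each arm, and both ratios are 0.99 to 1.01.

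**5. The fold-rise alternative.** exp[mean(log post − log baseline)] is defined for everyone: no rise gives 1, and a one-dilution fall gives 0.5.

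**The case against.** A reader might infer that the plan removes uninfected participants from the table, and more of them from the vaccine arm. The documents do not support that reading.

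- No text says non-positive changes are dropped. SAP 5.3.5, under outliers, says all measured values are analysed. The same table also carries n, SD, median, minimum and maximum, which can include zeros and falls. Only the geometric mean and its CI fail. A programmer could also read the logged data as a log difference, which removes the problem, and the SAP 3.0 entry in the change list (6.3) ties the geometric mean to tables where it must appear.
- A higher share lost among vaccinees needs efficacy against infection. The primary endpoint is viral shedding (vAUC), and the protocol pairs 83% with 30% efficacy only to illustrate the correlate analysis.
- No rise and uninfected are different groups: assay variation gives some uninfected a rise, and some infected show none.
- The ratio in SAP 2.2.4 need not be a ratio of changes. Protocol 9.1.2.3 describes a ratio of GMTs, and SAP 2.2.3 a ratio from log titres. Both are sound.

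All of this limits the consequence. It does not remove the conflict. Including all measured values is exactly what a geometric mean of raw differences cannot do. The log-difference reading is the sensible one, but SAP 5.2.2 states a subtraction of values, and where the SAP wants the log scale for antibody it says so, in 2.2.3.

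**Conclusion.** The point holds as a conflict between stated rules: the geometric mean and CI in Table 14.2.4.5 are undefined for zero or negative changes, which half-limit imputation and low entry titres make likely, and the SAP gives no rule for them.

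The masking of a difference between arms is conditional. It requires that non-positive values are set to missing and that the vaccine lowers the infection rate. Under both, at 83% and 30%, the ratio of geometric mean changes would be 0.83 to 1.00 where the fold-rise ratio is 0.50 to 0.72; with one-dilution assay noise, the more realistic case, it is 0.83 to 0.91. These figures rest on assumed titres and rises, and matter only if an arm ratio of changes is shown or read from the table. At 0% efficacy there is no distortion between arms.

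One descriptive table of an exploratory endpoint is affected. No primary or secondary conclusion depends on it, and the titre table (14.2.4.4), the ratio of GMTs and the log-titre ANCOVA stand.

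**What to change.** Add one sentence to SAP 5.2.2 or 2.2.2: for MNT and HI, change from baseline is the log titre at Day 28 post-challenge minus the log challenge-baseline titre, back-transformed and reported as a geometric mean fold-rise with 95% CI.

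In Table 14.2.4.5, show this with n per arm for all participants who have both samples, and relabel the table as fold-rise. State that any arm ratio shown there is the ratio of fold-rises, and keep the protocol's ratio of GMTs for the actual-value table, so that SAP 2.2.4 is no longer open to two readings.

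The cost is the sentence, a relabelled table and a small programming change. No new data are needed, and the scale then matches the log10 GMT comparison in Protocol 9.1.2.3 and the ANCOVA in SAP 2.2.3.

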5.4.3 Ordering in tables, figures and listings

All tables will be presented per treatment, unless specified otherwise.

All listings will be ordered by treatment, subject, analysis visit and time point, unless specified otherwise.

	Statistical Analysis Plan	
FLU010	Final analysis	Final 3.0 of 15JUN2020

6. CHANGES TO THE PLANNED ANALYSIS

6.1 CHANGES NOT COVERED BY PROTOCOL AMENDMENTS BEFORE DATABASE LOCK

NAP

6.2 CHANGES NOT COVERED BY PROTOCOL AMENDMENTS AFTER DATABASE LOCK

NAP

6.3 CHANGES TO THE FINAL STATISTICAL ANALYSIS PLAN

SAP version number	SAP version Date (ddMMMyyyy)	Changes
Final 2.0	08MAY2020	
Definition of terms: "treatment-emergent abnormality": Clarification has been added that abnormalities in vaccination phase are evaluated versus vaccination baseline and post-challenge abnormalities are evaluated versus challenge baseline.

		
Section 2.1.2: Derivation rule for "Time to feel well enough to go to work (hours)": Censoring on the last assessment will not only occur for subjects not having any positive answer, but for any subject having a negative answer as last assessment.

		
Section 2.2.1: Instead of four, only three stimulation antigens will be assessed with the ELISpot assay: NP, M1 and DMSO (not NP+M1). It has also been clarified that the results will be reported in SFC per well (i.e. 200,000 cells) for two replicate wells. Clarification has been added that only MNT is done at screening.

	Statistical Analysis Plan	
FLU010	Final analysis	Final 3.0 of 15JUN2020

SAP version number	SAP version Date (ddMMMyyyy)	Changes
		
Section 2.2.2:
 
Derivation rules for background subtracted T cell response result has been changed to account for the fact that each peptide pool contains a different set of peptides and may therefore have a different response profile. Results can therefore not be averaged over pools. Therefore, background subtracted results must first be calculated per pool. If negative, these background subtracted results must be set to 0. The background subtracted T cell response result for a specific antigen (either NP or M1) is the sum of the background subtracted results of the pools within that antigen (4 pools for NP and 2 pools for M1).
 
A derivation rule has been added for the negative control T cell response results (missing from previous SAP version):
 
The negative control T cell response result is the result aver all replicates.
 
Derivation rule for T cell responder status has been changed to specify that the derivation should be applied for each of the antigens NP and M1 separately and to clarify that an unadjusted p-value and a permutation-adjusted p-value will be calculated for each peptide pool, instead of for each antigen.
 
Furthermore, the unadjusted p-value will not be calculated using a Mann-Whitney U Test, but using a two-sample t-test.
 
Responder status cannot be determined if results from only one negative control well are available, but the same also applies to the peptide pools results.
 
Finally, to come to the T cell responder status, since the permutation-adjusted p-values are calculated per pool, an additional step has been added to specify that a subject will be considered a responder if a permutation-adjusted p-value of any of the pools within the antigen is less than 0.05.

	Statistical Analysis Plan	
FLU010	Final analysis	Final 3.0 of 15JUN2020

SAP version number	SAP version Date (ddMMMyyyy)	Changes
		
Section 2.2.4:
 
Specification has been added that next to background subtracted T cell response, the negative control T cell response results will also be summarised by means of descriptive statistics at each analysis visit.
 
Similarly, graphs of the median actual values over time will also be prepared for negative control results.

		
Section 5.1.1:
 
"Per-protocol set (PP)":
 
Major protocol deviations may also contain deviations not having impact on the primary endpoint. Therefore, rather than excluding subjects with any major protocol deviation, this specification has been updated to only exclude subjects with major protocol deviations impacting the primary endpoint.
 
A programmer note has been added that major protocol deviations impacting the primary endpoint will be flagged as such in the database.

		
Section 5.3.3
 
Imputation rules have been added for immunogenicity values below or above a threshold:
 
Immunogenicity values reported as > XX will be imputed with XX. Immunogenicity values reported as < XX will be imputed with XX/2.

		
Section 8.1:
 
Title of table "Influenza Symptoms - General SSC Score Changes Mixed Model for Repeated Measures" has been corrected to "Influenza Symptoms - Overall SSC Score Changes Mixed Model for Repeated Measures". To keep a logic order of TLFs, the number has been changed from 14.2.3.15 into 14.2.3.11.
 
Therefore, numbers of tables 14.2.3.11 to 14.2.3.14 in previous SAP version have been incremented.

	Statistical Analysis Plan	
FLU010	Final analysis	Final 3.0 of 15JUN2020

SAP version number	SAP version Date (ddMMMyyyy)	Changes
		Section 8.3: Title of figure “Log qPCR Mean Adjusted Changes vs. Time Profiles” has been corrected to “Log qPCR Mean Adjusted Actual Values vs. Time Profiles”.
		Section 9.1: Proc multtest in sample code for “Permutation-based Resampling Method” has been adjusted to perform 20,000 instead of 20,000 permutations, and to be processed by subject and timepoint instead of only by subject.
Final 3.0	15JUN2020	Section Definition of terms: Details have been added to clarify the meaning of 'within two consecutive days'.
		Sections 2.1.2.2 and 2.1.2.3: For endpoint 'Time to start of viral shedding' it was specified that the first positive sample to be considered for the time calculation is the first of two consecutive samples, as this is also the event. Similar clarification was added for duration of viral shedding, time to start of symptoms and duration of symptoms
		Section 2.2: After expert input and on request of the sponsor, it has been decided that T-cell response analysis needs to be done on two subsets of samples. The restrictive rule of needing at least two replicates for the derivation of response status has been removed in section 2.2.2. The definition of both subsets has been added in section 2.2.4.
		Section 5.4.1: It has been specified that geometric mean will replace arithmetic mean in tables where it has to be shown.
		Section 9.1: A seed has been specified in the code of the proc multtest to allow reproduction of the results.

	Statistical Analysis Plan	
FLU010	Final analysis	Final 3.0 of 15JUN2020

